6. STATISTICS AND DATA ANALYSIS

Statistical analyses and data management will be conducted by specialist staff, in accordance with a pre-specified Statistical Analysis Plan, at the Boden Collaboration, University of Sydney.

The Boden Collaboration will build a database (in RedCap) for the DiRECT study. All data will be entered by the 5 x dietitians from the 5 x PHNs. They will be given unique password protected logins. The Boden Collaboration will oversee the data collection and integrity.

Through specific data identifiers, the data from the DiRECT study can then be linked with the Lumos data linkage project administered by the NSW Government, Department of Health.

The main objective of the study is to determine if a VLED and structured weight management program can be instituted as effectively in primary care in Australia as in the original UK DiRECT trial.

Data will be analysed primarily on an intention-to-treat (ITT) basis with last observation carried forward data on weight and diabetes status for subjects who discontinue the formal weight management program. A 'completers analyses' of participants completing the study will also be performed. Trial documentation and data will be retained for at least 15 years after study completion.

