TDR	Total Diet Replacement
GIG	Governance and implementation Group

STUDY SYNOPSIS

[figure not shown]
Title of Study:	Diabetes REmission Clinical Trial-Aus; DiRECT-Aus
Study Centre:	University of Sydney
Duration of Study:	Active intervention: 12 month per subject Follow up: 4 years after completion of active intervention
Primary Objective:	
To determine whether a program, designed to achieve remission of T2DM to normal glucose tolerance by substantial weight loss using a very low energy diet (VLED), can be effectively delivered within the routine primary care setting where most people with T2DM are managed in Australia.
 
The Diabetes Remission Clinical Trial (DiRECT) was a study funded by Diabetes UK that tested whether a low calorie-based weight management program, delivered in primary care could result in long term Type 2 diabetes remission. Diabetes UK, the University of Glasgow and Newcastle University have since developed the DiRECT principles, which set out the core elements of health intervention to have the best chance of replicating the outcomes of the DiRECT study.
 
This project intent is to replicate or better the remission results achieved in the UK DiRECT study for people with T2DM in the participating PHN regions and undertaking the intervention in general practice.

Secondary Objective:	To evaluate the attitudes of participants to the VLED program including acceptability, ease of use and perceived value.
Primary Endpoint:	% of participants achieving a non-diabetic HbA1c (<6.5%; <48 mmol/mol) at 12 months having ceased all diabetes medication for at least the preceding 2 months
Rationale:	Bariatric surgery can convert 70-80% of people with T2DM to the non-diabetic state. The DiRECT trial provided evidence that T2DM could also be reversed by a strict energy restricted diet, with 10-15kg weight loss. The present study will determine if the results of the DiRECT trial can be replicated in an Australian primary care setting and establish whether it is possible to produce remission of T2DM at 12 months and sustain it over 5 years. An VLED can be provided relatively cheaply in the primary care setting where obesity and T2DM are managed, using a total diet replacement (TDR), such as Optifast, which is readily available to the Australian general public. The study will also assess quality of life and attitudes of subjects during the intervention.

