	
 • Myocardial infarction within previous 6 months • Learning difficulties which in the opinion of the investigator prevent the subject providing informed consent and complying safely with the diet • Use of weight loss agents or medications taken to primarily reduce weight (eg orlistat, lorcaserin, Qysmia, Contrave, GLP-1 receptor analogues, over the counter or herbal weight loss agents) within the past 3 months • Have ever been diagnosed with and eating disorder or engaged in purging behaviour • Pregnant/ considering pregnancy • people currently participating in another clinical research trial • Allergy to Optifast or any of its ingredients
Product, Dose, Modes of Administration:	
The intervention is a 3400kJ (800kcal)/day TDR, followed for 13 weeks, with stepped food reintroduction to long-term weight loss maintenance using a tested energy-restricted nutritionally balanced (30% fat, < 10% saturated fat) maintenance diet using food-group exchanges, and support for behaviour change. Physical activity will be encouraged with a recommendation of at least 30 minutes brisk-walking daily and aiming to reach and maintain an individual sustainable maximum with a target of 15,000 steps/day.
 
Participants will continue to receive standard care under current clinical guidelines for T2DM. Intention to treat analysis will be conducted, with follow-up data continuing to be collected even if treatment is stopped.
 
The intervention will be delivered in primary care practices by practice nurses/dietitians (according to local availability and practice) with training, support and mentoring from the Boden Collaboration, University of Sydney.

Duration of Treatment:	12 months. Subject to additional funding, at least annual follow up for 5 years
Statistical Analysis:	
Data will be analysed primarily on an intention-to-treat (ITT) basis, using last observation carried forward for weight and diabetes status for subjects who discontinue the formal weight management program or experience an adverse event.
 
A ‘completers analysis’ of participants who complete the study will also be performed.

STUDY FLOW CHART

Screening and Baseline appointments

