3.5 Withdrawal of subjects

Patients who withdraw from the study after commencement of participation in the study will continue to have data collected from their routine GP visits, unless they specifically withdraw consent for this. Data on weight and HbA1c recorded in GP notes within 3 months either side of the patients planned 12 months follow-up date will be used. Data analysis will use best available follow-up weights (from routine attendances) and end of study diabetes status for subjects who discontinue the formal weight management program.

Diet intolerance or poor-compliance will be recorded: these patients will be included in ITT analysis, but excluded in 'completers analyses'. The same procedures will be used to obtain the five year follow-up data.

4. Trial procedures

Practices will deliver an VLED phase followed by structured food reintroduction and long term weight loss maintenance. Training for the practice nurses/dietitians in VLED delivery, maintenance diet program and behaviour therapy will be provided by the Boden Collaboration, University of Sydney. Training for the practice nurses/dietitians in the maintenance diet program and behaviour therapy will be provided by Diabetes NSW & ACT. To increase access in regional areas, practices may deliver the intervention via telehealth but all participants will attend their GP practice for safety monitoring and collection of study data.

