4.1.3 Rescue Package for weight regain or re-emergence of diabetes

Many patients find weight maintenance difficult. Some patients relapse temporarily and gain weight rapidly and others may let things slip more gradually. Pilot studies showed the value of a sympathetic, but firm approach to relapse/regain management.

If weight regain occurs or if diabetes is found to have returned (HbA1c > 48 mmol/mol [6.5%]) at any time during the weight loss maintenance stage, 'rescue plans' for weight gain prevention will be offered:

- 1) **Weight regain of >2 and up to 4kg:** offer the use of Optifast to replace one main-meal per day for 4 weeks.
- 2) **Weight gain of >4kg or re-emergence of diabetes at any time:** offer 4 weeks VLED with fortnightly practice nurse/dietitian review and then a 2-4 weeks food re-introduction (adding 1 meal/week as before). Low-fat dietary advice and physical activity will be reinforced for weight maintenance.

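### Carrying diabetes status forward conflicts with the end-of-study rule in Section 3.5 and is likely to overstate 12-month remission, by an amount the protocol does not determine

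*Protocol*

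**What the plan says.** The primary endpoint (Synopsis; also Sections 2 and 4.5.1) is the percentage of participants with HbA1c below 6.5% "at 12 months having ceased all diabetes medication for at least the preceding 2 months".

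Three places say how participants who stop the programme enter the analysis:

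- **Section 6**, for the primary intention-to-treat analysis: "last observation carried forward data on weight and diabetes status for subjects who discontinue the formal weight management program".
- **Synopsis, Statistical Analysis**: the same rule with a wider trigger, "using last observation carried forward for weight and diabetes status for subjects who discontinue the formal weight management program or experience an adverse event".
- **Section 3.5**: the analysis uses "end of study diabetes status for subjects who discontinue the formal weight management program", and for records data, "Data on weight and HbA1c recorded in GP notes within 3 months either side of the patients planned 12 months follow-up date will be used".

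The Synopsis also commits to an intention-to-treat analysis "with follow-up data continuing to be collected even if treatment is stopped". No text ranks these rules, for example by limiting carry-forward to participants with no data near month 12.

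**The concern.** Carry-forward and end-of-study status are different estimates for the same people. The first reports where a participant stood when last measured, which may be the end of the diet. The second reports where the participant stands near month 12, which is what the endpoint asks. The two differ when remission is lost in between, and the protocol does not treat remission as stable. Section 4.1.3 says "Many patients find weight maintenance difficult" and provides for re-emergence of diabetes, and Section 1.1 reports UK remission of 46% at 12 months and 36% at 2 years.

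Remission at 12 months is the only primary endpoint. The study has one arm, and Section 6 sets its aim as being as effective as the UK trial, so no control arm offsets an error of this kind. Two analysts following different sections could report different primary results from the same data.

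**Working it through.** The protocol states no expected remission rate, discontinuation rate or relapse rate, so it has no figure of its own to reproduce. The check has four steps.

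**1. Can an end-of-diet remission satisfy the definition?** Section 4.2.2 withdraws glucose-lowering drugs when the diet starts (week 0). Table 1 in Section 4.4 schedules HbA1c at the end of the diet (week 13) and at weeks 25, 37 and 52. A participant who has not restarted drugs has been off them for 13 × 7 = 91 days at week 13, against about 61 days for 2 months. HbA1c below 6.5% at that visit therefore meets both parts of the definition, and carry-forward would extend it over 52 − 13 = 39 weeks.

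**2. Would Section 3.5 use such a value?** Three months is about 13 weeks, so its window for GP records runs from week 39 to week 65. The interim tests at weeks 13, 25 and 37 all precede it. Week 37 misses by only about two weeks, and the window is written for GP notes rather than scheduled trial tests, so little weight rests on that visit.

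**3. Who is affected?** A participant who leaves before the week-13 HbA1c carries forward baseline status. Under Section 3.2 that means HbA1c at or above 6.5%, or a lower value on medication. Neither is remission, so carry-forward does not inflate the rate for these participants. Only those leaving after the week-13 test matter.

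**4. How large could the excess be?** Let

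- d = share of all participants who leave after the week-13 HbA1c and have status carried forward;
- r = share of these in remission at their last HbA1c;
- q = share of those remitters who relapse by month 12;
- g = share of the non-remitters who remit later.

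Excess over true 12-month remission = d × [r × q − (1 − r) × g].

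All four are assumptions. The only related figure in the protocol is the UK fall from 46% to 36%, a net relative loss of (46 − 36)/46 = 22%. It covers a whole arm over the second year, so it is a rough guide for q at best. With r = 0.5 and g = 0, the excess in percentage points is:

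| d | q = 0.22 | q = 0.5 | q = 1.0 |
|---|---|---|---|
| 10% | 1.1 | 2.5 | 5.0 |
| 20% | 2.2 | 5.0 | 10.0 |
| 30% | 3.3 | 7.5 | 15.0 |

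For example, 0.20 × 0.5 × 0.5 = 5.0 points. Widening to d = 5-30% and r = 0.3-0.7 gives 0.3 to 21 points. With r = 0.5 and q = 0.22, the excess disappears if g is also 22%.

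For scale, the 95% half-width for 46% with n = 250, ignoring practice clustering, is 1.96 × √(0.46 × 0.54/250) = 6.2 points. The excess reaches that size only with substantial late discontinuation and relapse, for example 0.20 × 0.7 × 0.5 = 7.0 points.

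The choice of rule can also be compared directly. If d = 20%, r = 0.5 and 46% of everyone else is in remission, carry-forward gives 0.8 × 46% + 0.2 × 50% = 46.8%. Counting the same leavers as not in remission gives 0.8 × 46% = 36.8%.

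**The adverse-event trigger.** Section 5.1 records as adverse events, among others, capillary glucose above 15 or below 4 mmol/L, systolic pressure below 110 or above 140, and an HbA1c change of more than 1%. Read literally, the Synopsis would apply carry-forward to anyone with such an event, including participants who never left and have a week-52 HbA1c.

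**The case against.** The best defence is that the texts can be read together. Neither Section 6 nor the Synopsis says the last observation must precede discontinuation, and Section 3.5 keeps collecting routine data after withdrawal. A value near month 12 could then be the last observation, with earlier values carried only when nothing later exists. Section 6 also defers to a statistical analysis plan, which is not shown and may set that order. This is a sensible reading, and where Section 3.5 data are obtained and used there is no inflation. But the protocol does not state it. Even under it, a week-13 remission stands as a 12-month remission whenever no later record is found, and the adverse-event wording remains unexplained.

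A reader might infer that the primary result is inflated by a definite and large amount. The documents do not support that. They give no discontinuation or relapse rate, early leavers carry forward non-remission, and later remissions would offset part of any excess. Section 4.1.3 describes relapse during maintenance, so it says little directly about people who have left. The likely direction is upward; the size is unknown.

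A reader might also infer that drug status is left out for those who withdraw. Section 3.5's sentence on the window names only weight and HbA1c, but the next sentence calls for end-of-study diabetes status, which implies drug status. The wording needs to be made explicit; it does not show an omission. Carry-forward for weight, a secondary outcome, is not part of this point.

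**Conclusion.** The contradiction is established from the text: for the same participants, Section 6 and the Synopsis carry diabetes status forward, Section 3.5 uses end-of-study status, and no priority is given. It is also established that, read literally, the carry-forward rule can score a remission at week 13, 25 or 37 as a 12-month remission. From this it follows that 12-month remission is likely, not certain, to be overstated.

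The illustration of about 1 to 15 points rests on 10-30% leaving after the week-13 HbA1c, half of them in remission at that point, 22-100% of those relapsing, and no late remission among the rest. None of these values is in the protocol except the 22%, which is borrowed from a different period. The adverse-event wording in the Synopsis makes the problem worse. Because this concerns the sole primary endpoint of a single-arm study, it should be settled before the data are analysed.

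**What to change.** Reconcile the Synopsis, Section 3.5 and Section 6 to one order of use for diabetes status in the primary analysis:

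1. observed week-52 HbA1c and glucose-lowering drug status, whether or not the programme was stopped;
2. failing that, HbA1c and glucose-lowering drug status from GP records in the Section 3.5 window, stating that drug status is extracted as well;
3. failing both, not in remission.

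Delete the adverse-event trigger from the Synopsis. Keep carry-forward of diabetes status only as a labelled sensitivity analysis.

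The cost is wording in three places and one more field in the record extraction. The reported remission rate may be somewhat lower. Step 3 is deliberately conservative: it counts as failures any participants still in remission for whom no record exists. With g = 0 that shortfall is d × r × (1 − q), where d now covers only leavers without usable data. At d = 20%, r = 0.5 and q = 0.5 it is 0.20 × 0.5 × 0.5 = 5.0 points. Obtaining the GP records keeps it small, and the carry-forward sensitivity analysis shows how much the result depends on it.

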7.0 STUDY CLOSURE / DEFINITION OF END OF TRIAL

The intervention and follow up period for each trial participant will last for 12 months with the possibility of extending to a total of 5 years if additional funding is secured. The initial 12 month study period will continue for a further 6 months to allow final data analysis, write up of final report and preparation of publications.

8. DATA HANDLING

8.1 Case Report Forms

A case report form (CRF) will be used to collect study data. The CRF will be developed by the Boden Collaboration in conjunction with Diabetes NSW/ACT with input from study practices. Remote Data Capture (REDCap) will be used for data entry and storage. Access to the pooled CRF data will be restricted, with only authorised site-specific personnel able to make entries or amendments to their patients' data.

Data will be validated at the point of entry into the CRF and at regular intervals during the study. Data discrepancies will be flagged to the study site and any data changes will be recorded in order to maintain a complete audit trail (reason for change, date change made, who made change).

8.2 Record Retention

To enable evaluations and/or audits from regulatory authorities, the investigator agrees to keep records, including the identity of all participating subjects (sufficient information to link records), all original signed informed consent forms, serious adverse event forms, source documents, and detailed records of treatment disposition in accordance with Ethic Committee requirements.

All data received via study secure web portal will be stored on a secure database and any original files received from third parties will be stored in their received format in secure file storage. Data will be held for a minimum of 15 years

10. PROTOCOL AMENDMENTS

Any change in the study protocol will require an amendment. Variations in the durations of the treatment phases, within the limits described in Section 4 above, will not require an amendment. Any proposed protocol amendments will be initiated by the CI and submitted to the ethics committee and sponsor. The CI will liaise with study sponsor to determine whether an amendment is non-substantial or substantial. All amended versions of the protocol will be signed by the CI and Sponsor representative. Before the amended protocol can be implemented favourable opinion/approval must be sought from the Ethics Committee.

11. ETHICAL CONSIDERATIONS

The study will be carried out in accordance with the World Medical Association Declaration of Helsinki (1964) and its revisions (Tokyo [1975], Venice [1983], Hong Kong [1989], South Africa [1996] and Edinburgh [2000]).

Favourable ethical opinion will be sought from an appropriate Ethics Committee before patients are entered into this study. Patients will only be allowed to enter the study once they have provided written informed consent. The CI will be responsible for updating the Ethics committee of any new information related to the study.

12. INSURANCE AND INDEMNITY

In SNHN Services Agreement with Diabetes NSW/ACT

The Liability Minimum Limit \$20,000,000 for any one occurrence in the annual aggregate

Professional Indemnity Minimum Limit \$20,000,000 for any one occurrence in the annual aggregate

13. FUNDING

Primary Health Networks to contribute \$114,000 per PHN (5) = \$570,000

Diabetes NSW/ACT \$188,991 plus GST of \$18,899

14. ANNUAL REPORTS

Annual reports will be submitted to the ethics committee with the first submitted one year after the date that all trial related approvals are in place.

APPENDIX A: DiRECT-Aus SCHEDULE OF ASSESSMENTS

		Total Diet Replacement Phase								Food Reintroduction Phase		
Appointment		1	2	3	4	5	6	7	8	9	10	11
Week		-2	0	1	3	5	7	9	11	13	15	17
Study Procedure	Responsibility											
Review & discuss study participation	GP/nurse/dietitian	√										
Obtain Informed Consent	GP/nurse/dietitian	√										
Review Inclusion/Exclusion Criteria	GP	√										
Collect medical history	GP/nurse/dietitian	√										
Record medications	GP/nurse/dietitian	√	√	√	√	√	√	√	√	√	√	√
Height	Nurse/dietitian	√										
Weight	Nurse/dietitian	√	√	√	√	√	√	√	√	√	√	√
Waist Circumference	Nurse/dietitian	√	√	√	√	√	√	√	√	√	√	√
Hip Circumference	Nurse/dietitian	√										
Blood Pressure	Nurse/dietitian	√	√	√ ^a	√ ^a	√ ^a	√ ^a	√ ^a	√ ^a	√ ^a	√ ^a	√ ^a
Blood & urine samples	Pathology	√										
Hypoglycemic agents discontinued	Nurse/dietitian ^b		√									
Capillary blood glucose	Nurse/dietitian		√	√ ^c	√ ^c	√ ^c	√ ^c	√ ^c	√ ^c	√ ^c	√ ^c	√ ^c
Repeat HbA1c	Pathology									√		
EQ-5D questionnaire	Participant		√							√		
Binge Eating Questionnaire	Participant		√							√		
Food Acceptability Questionnaire	Participant		√							√		
Baecke Physical Activity	Participant		√							√		
Record steps previous two weeks	Nurse/dietitian		√ ^c							√		
Urine pregnancy test	Nurse/dietitian	√										
Adverse events monitoring	Nurse/dietitian		√	√	√	√	√	√	√	√	√	√

Schedule of Assessments (continued)

		Weight Maintenance Phase (Year 1)									
Visit		12	13	1	15	16	17	18	19	20	
Week		21	25	29	33	37	41	45	49	0+52	
Study Procedure											
Record medications		√	√	√	√	√	√	√	√	√	
Height										√	
Weight		√	√	√	√	√	√	√	√	√	
Waist Circumference		√	√	√	√	√	√	√	√	√	
Hip Circumference										√	
Blood Pressure		√ ^a	√ ^a	√ ^a	√ ^a	√ ^a	√ ^a	√ ^a	√ ^a	√ ^a	
Blood & urine samples										√	
Capillary blood glucose		√ ^c	√ ^c	√ ^c	√ ^c	√ ^c	√ ^c	√ ^c	√ ^c	√ ^c	
HbA1c			√			√				√	
EQ-5D questionnaire										√	
Binge eating scale										√	
Food Acceptability Quest.										√	
Baecke Physical Activity										√	
Record steps previous two weeks										√	
Urine pregnancy test										√	
Adverse event monitoring		√	√	√	√	√	√	√	√	√	

^a Blood pressure medication reduced if BP <110/60 mmHg or reintroduced if BP subsequently >140/90 mmHg

^b GP to make medication adjustment if capillary blood glucose > 15mmol/L

^c hypoglycaemic agents reintroduced if capillary blood glucose >15 mmol/L or HbA1c >9% or >1% change from last measurement

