4.1 Diet intervention

4.1.1 VLED phase (0-13 wks): A commercial micronutrient-replete VLED (3400 kJ (800 kcal)/day) will be provided (Optifast, Nestle Health Science) to replace normal meals along with ample fluids and low starch vegetables for 13 weeks. Participants will be required to add 1 teaspoon of olive oil daily (to assist with gall bladder contraction and thereby reduce the chance of biliary complications) and may add a psyllium husk based fibre supplement if constipation develops. Participants with a BMI >40 kg/m² will have an additional meal replacement product with the goal of preserving lean body mass during weight loss.

Participants will return for review one week after commencement of the VLED and at two weekly intervals thereafter until week 13 (total of 7 appointments) and the commencement of the food reintroduction stage.

To allow some flexibility for patients whose commitments vary, the VLED phase may be permitted to continue up to 21 weeks. Any patient whose BMI falls below 23 kg/m² before week 13 will be moved forward to the 'food reintroduction and weight maintenance' phase. Reasons for moving to food reintroduction before week 13 will be recorded.

Food Reintroduction phase (weeks 13-18):

A stepped transition to food-based Weight Maintenance in which the VLED will be gradually replaced with meals that contain 30% of energy from fat. During this phase participants will attend for review appointments every 2 weeks.

Week 13: step down to 2 Optifast meal replacement products per day + 1 low-fat meal/day + 2 servings of fruit, 1 serve low fat dairy and free (low starch) vegetables. Total intake 4200kJ (1000kcal)/day.

Week 15: step down to 1 Optifast meal replacement product per day + 2 low-fat meals/day + 2 servings of fruit, 2 serves low fat dairy and free vegetables. Total intake will 5000kJ (1200kcal)/day.

Week 17: 3 low-fat meals per day + 2 servings of fruit, 2-3 serves low fat dairy and free vegetables. Total intake 6000kJ (1400kcal)/day.

To allow flexibility for patients whose confidence varies, the food introduction phase will be permitted to be varied between the protocol-defined limits of 2-8 weeks before switching to full food-based weight maintenance. Reasons for moving to weight loss maintenance without completing food reintroduction will be recorded.

4.1.2 Weight Maintenance Phase (weeks 21-52):

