4.6 Study schedule

Eligibility for the study and reintroduction of blood glucose lowering and blood pressure lowering medication, if required, will be determined by the GP. All other aspects of the study appointments may be delegated to the study dietitian or nurse according to local preferences and where the study dietitian and/or nurse are willing and able to perform the procedures in the GP's opinion. The GP will be available for discussion and guidance if required by the study dietitian or nurse.

Appointment (Appt) 1 (Week -2): Screening

- Review and discuss study participation
- Secure informed consent
- Assign study ID,
- Eligibility check performed by GP
- Record medical history and medications
- Measurement of: height, weight, waist & hip circumference & blood pressure
- Provide request form for fasting blood test and urine test to be completed prior to the baseline visit: HbA1c, glucose, urea & electrolytes, creatinine, eGFR, CaPO₄, magnesium, liver function tests, lipids, full blood count and urine sample for albuminuria
- Perform Urine pregnancy test in women of childbearing potential
- Advise patient that two week step count monitoring will be collected at next visit

Appt 2 (Week 0) Baseline

- Collect 2 weeks record of daily steps
- Measurement of weight, waist circumference, blood pressure and capillary blood glucose (measured by blood glucose meter)
- Record any changes to medications
- Record any adverse events
- Hypoglycaemic medications discontinued. If capillary blood glucose > 15mmol/L the GP will determine what actions to be taken with hypoglycaemic medications.
- Antihypertensive medications reduced or ceased only if BP <110/60

- Commence VLED phase of intervention
- Questionnaire completion: EQ-5D, Binge Eating Disorder, Beacke Physical Activity and Food Acceptability Questionnaire
- Provide 1 week supply of Optifast and instructions for ordering Optifast

Appt 3-9 (Weeks 1-13): Continue VLED

- Measurement of weight, waist circumference & blood pressure
- Capillary blood glucose measured by blood glucose meter
- Record any changes to medications
- Record any adverse events
- Continue VLED intervention
- Check participant supply of Optifast

Appt 9 (Week 13) - Food reintroduction

- Begin structured food reintroduction (Step 1)
- Provide request form for non-fasting blood test to be completed within 2 days of appointment: HbA1c
- Measurement of weight, waist circumference & blood pressure

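### No pregnancy test is required before the 800 kcal/day diet is extended past week 13 or restarted as a 4-week rescue

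*Protocol*

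**What the plan says.** Section 3.3 excludes women who are pregnant or considering pregnancy. Section 3.2 requires women of childbearing potential to be ready and able to use contraception with a failure rate below 1% per year under consistent and correct use.

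For Appt 1 (week -2), Section 4.6 says "Perform Urine pregnancy test in women of childbearing potential". It lists no pregnancy test at any later visit. In Appendix A the row "Urine pregnancy test" has two ticks, at Appt 1 and at Appt 20 (week 52), so the two places disagree about week 52. Review of the inclusion and exclusion criteria is ticked at Appt 1 only.

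The diet is given or prolonged at three points:

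- **Start.** The Appt 2 (week 0) list includes "Commence VLED phase of intervention".
- **Extension.** Section 4.1.1 allows flexibility: "the VLED phase may be permitted to continue up to 21 weeks".
- **Rescue.** Section 4.1.3 sets the trigger as "Weight gain of >4kg or re-emergence of diabetes at any time", and the action is to "offer 4 weeks VLED with fortnightly practice nurse/dietitian review". This applies throughout the maintenance stage.

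Section 4.1.1 does contain one rule that ends the VLED early. It begins "Any patient whose BMI falls below 23" and moves the patient on to food reintroduction. Other early moves are foreseen: "Reasons for moving to food reintroduction before week 13 will be recorded".

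**The concern.** The protocol treats pregnancy as a reason not to give this diet and checks for it once before the first course. An extension and a rescue are new decisions to give the same diet, taken months later, and neither repeats the check. A woman who has conceived without knowing it could be kept on or put back on 800 kcal/day. The week-52 test comes after that exposure, so it can find a pregnancy but cannot prevent the exposure.

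The rescue is the more important of the two, because the last test is usually oldest there. As general clinical reasoning, which the protocol does not state, the rescue triggers (weight gain above 4 kg, or returning hyperglycaemia) could themselves reflect an unrecognised pregnancy.

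What is at stake is the protection of a small number of participants, not the analysis.

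**Working it through.** **1. Age of the last test, from the schedule alone.** The last test is at week -2, so its age at week *w* is *w* + 2 weeks.

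| Decision | Week | Age of last test |
|---|---|---|
| VLED start (Appt 2) | 0 | 0 + 2 = 2 weeks |
| Extension (Appt 9) | 13 | 13 + 2 = 15 weeks |
| Rescue, shortest standard path | 13 + 2 = 15 | 15 + 2 = 17 weeks |
| Rescue at the first scheduled maintenance visit (Appt 12) | 21 | 21 + 2 = 23 weeks |
| Rescue at the last monthly visit (Appt 19) | 49 | 49 + 2 = 51 weeks |

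The 17-week row uses the lower limit of 2 weeks for food reintroduction in Section 4.1.1, which lets maintenance begin at week 15. A patient moved forward before week 13 because BMI fell below 23 could reach maintenance sooner, and the gap would then be under 17 weeks. So 23 weeks is the gap at the first scheduled maintenance visit, not the minimum.

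**2. Conceptions in those windows.** Inputs:

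- Annual rate *r* = 1%, the protocol's ceiling under correct use. A rate of 5% for imperfect use is an assumption, shown for range.
- Number of women of childbearing potential *N*: not given. Assumed to be 10% to 40% of 250, which is 25 to 100.
- Formula: *N* × *r* × (weeks since last test) / 52.

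Per 100 women who reach the decision:

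- Extension, 15 weeks: 100 × 0.01 × 15/52 = 0.29; at 5%, 1.44.
- Rescue, 17 weeks: 100 × 0.01 × 17/52 = 0.33; at 5%, 1.63.
- Rescue, 51 weeks: 100 × 0.01 × 51/52 = 0.98; at 5%, 4.90.

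For the whole trial at 1%, if every such woman reached the decision:

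- Extension: 25 × 0.01 × 15/52 = 0.07, to 100 × 0.01 × 15/52 = 0.29.
- Rescue: 25 × 0.01 × 17/52 = 0.08, to 100 × 0.01 × 51/52 = 0.98.

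Even the extreme case, 100 women all rescued at week 49, stays below one conception at 1% per year. It would not at 5%.

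**3. How to read these figures.** They lean high: not every woman will be extended or rescued, some pregnancies would already be recognised, and the most recent would not yet show on a test. They are not strict upper bounds, because a conception shortly before week -2 may be missed at screening and is not counted.

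**4. The Appt 2 gap for comparison.** 100 × 0.01 × 2/52 = 0.04 per 100 women (0.19 at 5%). This is the smallest component, subject to the same caveat about very early pregnancies.

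**The case against.** The strongest reply is that the protocol already handles pregnancy and that more testing is a matter of preference. Pregnant women are excluded, highly effective contraception is required, and a test is done before the diet starts. Adverse events and medications are reviewed at every appointment: two-weekly for most of the VLED, and fortnightly under rescue. Findings that pose a risk go to the GP, stopping study treatment is a recorded action, and congenital abnormality is a serious adverse event criterion with notice to the Principal Investigator within 24 hours. The expected number of conceptions is below one at the protocol's own rate.

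Much of this stands, and it is why the point is minor. It does not close the gap. The contraception criterion is a condition of entry, and its rate assumes correct use. Adverse-event questions are deliberately non-leading and cannot reveal a pregnancy the woman does not know of. The serious adverse event route acts after harm.

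Three stronger readings are tempting and not supported:

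- *That women start the diet without a meaningful check.* The screening test is 2 weeks old at Appt 2, so this is the weakest part of the gap.
- *That the protocol leaves pregnancy unmanaged.* The safeguards above are written in. The consent pages, Section 9 and the study flow chart are not visible in the copy reviewed, so instructions to participants cannot be judged.
- *That the remission result would be affected.* Nothing in the documents points to this, and the numbers are too small to suggest it.

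**Conclusion.** The point holds in a limited form. Appendix A and Section 4.6 leave no pregnancy check between week -2 and week 52, so the VLED can be extended on a test 15 weeks old, or restarted on one about 17 to 51 weeks old (possibly less than 17 after an early move). The ages follow from the protocol's own schedule and phase limits. The expected count, below one conception in the trial, rests on an assumed 25 to 100 women of childbearing potential and on the 1% per year ceiling; with poorer contraceptive use it could exceed one.

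This is a rare but potentially serious safety matter with a very cheap remedy. The change is worth making, and the study does not depend on it. The visible text also names no specific action after a positive test, and the week-52 test is missing from the Appt 20 list in Section 4.6, which is an editorial mismatch.

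**What to change.** For women of childbearing potential:

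1. In Section 4.1.1, require a negative urine pregnancy test at Appt 9 (week 13) before any extension of the VLED.
2. In Section 4.1.3, require one before each 4-week rescue VLED. The lighter rescue step, which replaces one meal a day, does not need it.
3. Beside the BMI rule in Section 4.1.1, state that a positive test ends the VLED, prompts medication review by the GP, and is reported to the Principal Investigator.
4. Add the week-52 test to the Appt 20 list in Section 4.6 to match Appendix A, and add the new tests to both places.

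A repeat test at Appt 2 is optional. It would add 25 to 100 tests on the assumed range, for a small yield.

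The cost is one urine test per extension or rescue. Section 4 has all participants, including those on telehealth, attend the practice for safety monitoring, so no new visit is needed. Conceptions that arise while a VLED course is under way would still depend on contraception, adverse-event questions and GP review.
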